9.1.10 Pregnancy

Women of childbearing potential will not be included in this study.

If any subject is found to be pregnant during the study she should be withdrawn and any sponsor-supplied drug (TAK-831) should be immediately discontinued. In addition, any pregnancies in the female partner of a male subject during the study or for 95 days after the last dose of study drug should also be recorded following authorization from the subject's partner.

If the pregnancy occurs during administration of active study drug, for example, after Day 1 of Period 1 or within 95 days of the last dose of active study drug, the pregnancy should be reported immediately, using a pregnancy notification form, to the contact listed in Section 1.0.

If the female subject or female partner of a male subject agrees to the primary care physician being informed, the investigator should notify the primary care physician that the female subject/female partner of the subject was participating in a clinical study at the time she became pregnant and provide details of treatment the subject received.

All reported pregnancies, including those in female partners of male subjects, will be followed up to final outcome, using the pregnancy form. The outcome, including any premature termination, must be reported to the sponsor. An evaluation after the birth of the child will also be conducted.

9.1.11 ECG Procedure

Standard 12-lead ECGs will be recorded. When an ECG is scheduled at the same time as the blood draws or vital signs, then the blood draws and vital signs will take priority and the ECG will be obtained within 0.5 hours before or after the scheduled blood draw or vital sign assignment. If an ECG coincides with a meal, the ECG will take precedence followed by the meal.

All 12-lead ECG machines will be supplied by the study site. Subjects should be in a supine position following an approximate 5-minute rest period for ECG recordings. Should technical difficulties occur during recording of the ECG, a reasonable attempt should be made to repeat the ECG shortly after the failed attempt.

The investigator (or a qualified observer at the study site) will manually interpret the ECG using 1 of the following categories: within normal limits, abnormal but not clinically significant, or abnormal and clinically significant. The time that the ECG was performed will be recorded. The following parameters will be calculated automatically by the ECG machine and recorded on the eCRF: heart rate, RR interval, PR interval, QT interval, QRS interval, QT interval with Bazett correction method (QTcB), and QTcF interval. QTcF interval may be calculated manually by the study site. The QTcF interval is calculated as shown below:

$$QTcF = \frac{QT}{\sqrt[3]{RR}}$$

One copy of the 12-lead ECG with the physician's signature and date of assessment will be filed with the source documents and captured in the appropriate eCRF. If the original ECG is printed on

thermal paper, the ECG report must be photocopied and certified. The photocopy will be filed with the original ECG in the source. The study site uses a fully validated ECG system. The investigator assessment is recorded electronically within this system.

9.1.12 PGx Sample Collection

DNA forms the basis for the genes that make the body produce proteins such as enzymes, drug transporters, or drug targets, and may be evaluated for the genetic contribution to how the drug is broken down or how the drug affects the body. This is called a “PGx research study.” Specific purposes of this study include the following:

- Identifying genetic reasons why certain people respond differently to TAK-831.
- Finding out more information about how TAK-831 works.
- Generating information needed for research, development, and regulatory approval of tests to predict response to TAK-831.
- Identifying variations in genes related to the biological target of TAK-831.

This information may be used, for example, to develop a better understanding of the safety and efficacy of TAK-831 and other study drugs, and to improve the efficiency, design, and study methods of future research studies.

One 6-mL whole blood sample for DNA isolation will be collected at time point indicated in the Schedule of Study Procedures ([Appendix A](#)).

A portion of the DNA samples will be used to evaluate drug metabolic enzyme and transporter polymorphisms that may contribute to the variability in the PK of TAK-831. Also, since PGx is an evolving science, many genes and their functions are not yet fully understood. Future data may suggest a role of some of these genes in drug response, which may lead to additional hypothesis-generating exploratory research and diagnostic development on stored samples.

Detailed instructions for collecting, storing, handling, and shipping the PGx blood samples are provided in the laboratory manual.

9.1.13 PK Sample Collection

9.1.13.1 Collection of Blood for PK Sampling

Serial blood samples (one 4-mL sample per scheduled time) for PK analysis of TAK-831 will be collected into chilled Vacutainers containing the anticoagulant K₂EDTA, according to the schedule shown in [Table 9.b](#).

Table 9.b Collection of Blood Samples for PK Analysis

Analyte	Analysis Matrix	Dosing Day (Periods 1 and 2)	Time
TAK-831	Plasma	1	Predose (0 hour, within 15 minutes prior to dose) and 0.25, 0.5, 1, 1.5, 2, 3, 4, 8, 12, 24, 36, 48, and 72 hours postdose.

The actual time of sample collection will be recorded on the source document and eCRF.

Instructions for sample processing and shipment are provided in the laboratory manual.

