TAK-831 is a novel, highly selective and potent, small molecule inhibitor of D-amino acid oxidase (DAO), a peroxisomal enzyme active toward neutral D-amino acids, under development by Takeda for the treatment of various CNS disorders, including FRDA. In animal models, TAK-831

CCI

Additional information regarding the nonclinical pharmacology, pharmacokinetics (PK), and toxicology of TAK-831 is provided in the current Investigator's Brochure.

Two phase 1 studies have been conducted with TAK-831 in healthy subjects. The first study (TAK-831-1001) characterized the PK and pharmacodynamics (PD) of single-rising doses (SRD) (10 to 750 mg) and multiple-rising doses (30 to 400 mg) of a TAK-831 oral suspension, the relative bioavailability of an oral tablet (T1 formulation; 100 mg), and the effect of food (high-fat meal) on the tablet (100 mg). TAK-831 was absorbed rapidly following single and multiple doses of the oral suspension, with median time of first occurrence of C_{\max} (t_{\max}) values of 0.25 to 1 hour (range 0.17 to 2 hours). Exposure was generally dose dependent, with low intersubject variability (percent coefficient of variation [%CV] <40%). Corresponding mean terminal disposition phase half-life ($t_{1/2z}$) values ranged from 6 to 23 hours. Oral administration of a TAK-831 100 mg tablet with food increased TAK-831 exposure approximately 2-fold relative to administration without food. In the fasted state, exposure from the tablet was approximately 2-fold lower than that from the oral suspension. After single and multiple doses of TAK-831, changes from Baseline in D-serine area under the effect curve from time 0 to 24 hours (AUEC₂₄) were dose dependent.

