bioavailability of TAK-831 from the T2 tablet formulation. The objective of the current study is to estimate the magnitude of the food effect when TAK-831 (T2 tablet formulation) is co-administered with Ensure Plus (to be used in patients). Subjects will receive TAK-831 T2 tablets either in the fasted state or after ingesting Ensure Plus to evaluate the effect of this nutritional drink on the PK of TAK-831.

In the SRD study, the mean $t_{1/2z}$ values of TAK-831 ranged from approximately 6 to 23 hours over the 10 to 750 mg dose range, with the shorter mean $t_{1/2z}$ values generally occurring at the lower doses. Therefore, a washout interval of ≥ 7 days between the doses is sufficient to ensure that there is no drug carryover effect, and collection of PK blood samples up to 72 hours postdose is appropriate to characterize the PK of TAK-831.

The primary PK endpoints in this study, C_{max} and area under the plasma concentration-time curve (AUC), are standard PK parameters used to assess the effect of food on drug exposure. The use of standard noncompartmental PK parameters to assess the bioavailability of TAK-831 is well accepted in food-effect studies. Safety variables are included as the secondary endpoint (TEAEs) and exploratory endpoints ^{CCI} [REDACTED] to determine the tolerability of a single dose of TAK-831. These variables are routinely used for assessing safety and tolerability in clinical pharmacology studies. Additional exploratory endpoints are ^{CCI} [REDACTED]

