14.2 Protocol Deviations

The investigator should not deviate from the protocol, except where necessary to eliminate an immediate hazard to study subjects. Should other unexpected circumstances arise that will require deviation from protocol-specified procedures, the investigator should consult with the sponsor or designee (and IRB, as required) to determine the appropriate course of action. There will be no exemptions (a prospectively approved deviation) from the inclusion or exclusion criteria.

The site should document all protocol deviations in the subject's source documents, where applicable. In the event of a significant deviation, the site should notify the sponsor or its designee (and IRB, as required). Significant deviations include, but are not limited to, those that involve fraud or misconduct, increase the health risk to the subject, or confound interpretation of primary study assessment. A Protocol Deviation Form should be completed by the site and signed by the sponsor or designee for any significant deviation from the protocol.

The investigator should document all protocol deviations.

Every attempt will be made to collect each PK and PD blood sample at the designated time point, and the actual time of each blood sample will be recorded on the source document and eCRF. Blood samples not collected within the window specified for the scheduled sample time should be reported to Takeda using the Protocol Deviation Form. Protocol Deviation Forms are to be completed for PK/PD samples collected outside of the windows defined in [Table 14.a](#).

Table 14.a Windows for PK and PD Blood Sample Collection

Minutes	Nominal Sampling Time
≤30 minutes predose	0 hour
±5	immediately postdose to ≤6 hours
±10	>6 hours to ≤12 hours postdose
±15	>12 hours to ≤24 hours
±30	>24 hours

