- (j) FSH levels will be measured for female subjects when menopause is suspected and subject is not surgically sterile.
- (k) Pregnancy test will be performed for female subjects only.
- (l) 12-lead ECG will be performed at 1 hour, 2 hours, and 4 hours postdose.
- (m) One blood sample (6 mL) will be collected for DNA analysis before dosing on Day 1 of Period 1.
- (n) Blood samples (4 mL) for PK analysis will be collected at predose (within 15 minutes of dosing) and at 0.25, 0.5, 1, 1.5, 2, 3, 4, 8, 12, 24, 36, 48, and 72 hours postdose in each period.
- (o) Blood samples (6 mL) for PD analysis (D-serine and L-serine) will be collected on Day -1 at 24, 20, 16, and 12 hours before the Day 1 dose and on Day 1 at predose (within 15 minutes prior to dosing) and at 4, 8, 12, 24, 36, 48, 72, 120, and 168 hours postdose in each period. The 168-hour postdose sample for Period 1 may coincide with the 24-hour predose sample on Day -1 of Period 2, in which case 2 samples will be collected at the same time.
- (p) PTEs will be collected from the time the subject signs the informed consent until the subject is first administered study drug (Day 1 of Period 1) or until screen failure.
- (q) AEs will be collected from the time the subject is first administered study drug (Day 1 of Period 1) until the Follow-up Phone Call (Study Day 23 [\pm 2]).

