Clarifies that investigator may use clinical judgment when determining if abnormalities (even of shorter duration) make it necessary to withdraw subject from the study.

Change 2. Correction of inconsistencies in the description of contraception requirements.

The primary change occurs in Section 9.1.9.1 *Male Subjects and Their Female Partners*

Initial wording: From signing of informed consent, throughout the duration of the study, and for 95 days after the last dose of study drug, nonsterilized** male subjects who are sexually active with a female partner of childbearing potential* must use barrier contraception (eg, condom with spermicidal cream or jelly). In addition, they must be advised not to donate sperm during this period. Women of childbearing potential who are partners of male subjects are also advised to use additional contraception as shown in the list containing highly effective contraception below.

Amended or new wording: From signing of informed consent, throughout the duration of the study, and for 95 days after the last dose of study drug, nonsterilized** male subjects who are sexually active with a female partner of childbearing potential* must use barrier contraception (eg, condom with spermicidal cream or jelly). In addition, they must be advised not to donate sperm during this period. Women of childbearing potential who are partners of male subjects are also advised to use additional contraception as shown in the list containing highly effective contraception below. **If the female partner has been using 1 of the hormonal contraceptives methods listed below for >3 months, condom use is advised but not mandated.**

Rationale for Change:

Clarifies the intended requirements.

Change 3. Addition of extra ECG timepoints.

The primary change occurs in [Appendix A, Schedule of Study Procedures](#)

Initial wording: Footnotes for Appendix A:
...
(l) 12-lead ECG will be performed at 2 hours postdose.

Amended or new wording: Footnotes for Appendix A:
...
(l) 12-lead ECG will be performed at **1 hour**, 2 hours, **and 4 hours** postdose.

Rationale for Change:

Additional ECG measurements at 1 and 4 hours after dosing will extend these measurements to the expected time of C_{max} of the TAK-831 tablet.

Amendment 01 to An Open-Label, Single-Dose, 2-Period Sequential Design Phase 1 Study to Evaluate the Effect of Food on the Pharmacokinetics of TAK-831 Formulation T2 in Healthy Subjects

ELECTRONIC SIGNATURES

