## 7.9 Pharmacokinetic Analysis

### 7.9.1 Plasma Concentrations

Serial blood samples for determination of plasma concentrations of TAK-831 will be collected according to the table below:

Analyte	Matrix	Dosing Day (Period 1 and 2)	Scheduled Time (hours)
TAK-831	Plasma	1	Pre-dose (0 hour, within 15 minutes prior to dose) and 0.25, 0.5, 1, 1.5, 2, 3, 4, 8, 12, 24, 36, 48 and 72 hours post dose

The concentration of TAK-831 in plasma will be summarized by regimen at each scheduled sampling time using descriptive statistics (N, mean, median, SD, %CV, minimum, and maximum). Individual plasma concentration data versus time will be presented in a data listing.

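### Does the lack of a PK sample between 4 and 8 hours put the fed Cmax, and so the food-effect estimate, at risk?

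*Protocol*

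**What the plan says.** Protocol Table 9.b (Section 9.1.13.1) gives a predose sample and then "0.25, 0.5, 1, 1.5, 2, 3, 4, 8, 12, 24, 36, 48, and 72 hours postdose". Appendix A footnote (n) repeats the list for each period, and SAP Section 7.9.1 ends the same way: "3, 4, 8, 12, 24, 36, 48 and 72 hours post dose". The three places agree.

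On duration, Protocol Section 6.2 argues from half-life that "collection of PK blood samples up to 72 hours postdose is appropriate to characterize the PK of TAK-831". It does not discuss spacing around the peak.

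On peak time, the only numeric tmax is in Section 4.1 and belongs to the oral suspension: medians of 0.25 to 1 hour, range 0.17 to 2 hours. For the tablet there is one indirect statement, the rationale for Change 3 in Appendix E: "Additional ECG measurements at 1 and 4 hours after dosing will extend these measurements to the expected time of" the tablet's Cmax. Appendix A footnote (l) accordingly lists ECGs at 1, 2 and 4 hours after the dose.

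Cmax, AUClast and AUC∞ are the primary endpoints (Protocol 5.2.1, SAP 5.1). Cmax is the observed maximum (Table 9.c). The sample size is set on ln Cmax (Protocol 13.3, SAP 6.0), with an intrasubject CV of 37.5%, an assumed fed/fasted ratio of 2 and a 90% CI half-width of 0.23.

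**The concern.** An observed maximum can only be as high as the highest sample. If food delays absorption so that some fed peaks fall at 5 to 7 hours, the samples at 4 and 8 hours catch only the shoulders. Fed Cmax would then be too low, while an early fasted peak would be affected less, and the fed/fasted ratio would be biased downward in a study whose purpose is to estimate that ratio.

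The documents do not rule this out directly. The suspension is a different product: in the fasted state, tablet exposure was about half that of the suspension, and food roughly doubled tablet exposure (Section 4.1). Its tmax therefore does not show when fed tablet peaks end. The sponsor has fed data on the T1 tablet from Study TAK-831-1001, but the protocol prints no tmax from them. Table 14.a also has a ±5-minute window running "immediately postdose to ≤6 hours", although the last scheduled PK sample inside it is at 4 hours, which may suggest that a 6-hour draw was forgotten. A further draw would need only 4 mL per period while subjects are confined.

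**Working it through.** **1. Does the grid cover the expected peak?** The ECG times tied to the tablet's expected Cmax are 1, 2 and 4 hours. PK samples in that span fall at 1, 1.5, 2, 3 and 4 hours, with 0.25 and 0.5 hours before it. Appendix E names no hour, so a span of 1 to 4 hours is an inference, but it is the only indication for the tablet. The Table 14.a window is no sign of a missing draw: the table sets generic time bands for PK and PD samples together, and the PD times in Appendix A footnote (o) also go from 4 to 8 hours.

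**2. Yardstick: the plan's own precision.** Within-subject SD on the log scale: √ln(1 + 0.375²) = 0.363. With 14 completers and the normal quantile: 1.645 × 0.363 × √(2/14) = 0.2255, which rounds to the stated 0.23. Then 2 × exp(−0.23) = 1.589 and 2 × exp(0.23) = 2.517, as printed. With a t quantile on 12 df the half-width is 0.244, which does not alter the comparison.

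**3. Smooth profiles with a peak inside the gap.** One-compartment oral model, C(t) ∝ exp(−kₑt) − exp(−kₐt), with kₑ = ln 2 / half-life and kₐ solved from tmax = ln(kₐ/kₑ)/(kₐ − kₑ). Half-lives of 6 and 23 hours are the ends of the range in Section 4.1; 12 is an intermediate value. The true tmax values are assumed. Entries are the highest concentration on the planned grid divided by the true peak.

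| True tmax (h) | Half-life 6 h | 12 h | 23 h |
|---|---|---|---|
| 4 | 1.000 | 1.000 | 1.000 |
| 5 | 0.979 | 0.983 | 0.988 |
| 5.5 | 0.957 | 0.965 | 0.974 |
| 6 | 0.957 | 0.968 | 0.978 |
| 7 | 0.991 | 0.993 | 0.995 |

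If every fed subject lost the worst of these, a true ratio of 2 would read 2 × 0.957 = 1.91, a log shift of −ln 0.957 = 0.044. With a quarter affected: 2 × 0.957^0.25 = 1.98.

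**4. A distribution of fed tmax, smooth and sharp.** Assumed: lognormal fed tmax with log-SD 0.25; biexponential disposition (initial half-life 2, 4 or 6 hours; fast fraction 0.7 or 0.9; terminal half-life 23 hours). Sharp means a lag plus an absorption half-life of 0.6 hours; smooth means no lag, with the absorption rate solved for tmax. The share of peaks after 4 hours is 1 − Φ(ln(4/median)/0.25). Entries are geometric means of observed/true Cmax; gain is what a 6-hour draw would recover, in percentage points.

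| Median fed tmax (h) | Peaks after 4 h | Sharp: planned grid | Sharp: gain | Smooth: planned grid | Smooth: gain |
|---|---|---|---|---|---|
| 2 | 0% | 0.991–0.996 | 0.0 | 0.995–0.997 | 0.0 |
| 2.5 | 3% | 0.985–0.994 | under 0.2 | 0.994–0.996 | 0.0 |
| 3 | 12% | 0.974–0.991 | 0.2–0.9 | 0.995–0.996 | about 0.05 |
| 3.5 | 30% | 0.946–0.984 | 0.8–2.9 | 0.993–0.995 | about 0.2 |
| 4 | 50% | 0.903–0.972 | 1.8–6.2 | 0.990–0.992 | 0.4–0.5 |

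At a median of 3 hours the largest gain is ln(0.983/0.974) = 0.009 on the log scale, 0.009/0.23 = 4% of the planned half-width. Most of the loss there comes from spacing up to 4 hours, which a 6-hour draw leaves alone. The worst corner, median 4 hours and sharp, loses −ln 0.903 = 0.10, or 0.10/0.23 = 43% of the half-width, but it puts half of all fed peaks beyond 4 hours.

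**5. Net effect on the ratio.** Fasted peaks lose something on the same grid: observed/true 0.974 to 1.000, for an assumed sharp fasted peak with median tmax 0.75 to 1.5 hours. Pairing extremes at a fed median of 3 hours, a true ratio of 2 reads from 2 × 0.974/1.000 = 1.95 to 2 × 0.996/0.974 = 2.05. Even the direction is not fixed. Where the ratio reads above 2, a 6-hour draw that raised only the fed value would move it further from the truth.

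**The case for a change.** The strongest case for the concern is that the half-width of 0.23 measures random error, whereas missing late peaks is a systematic loss, so a small ratio between the two does not excuse it. The size also depends on shape. With a lag, rapid absorption and a fast initial decline, a single true peak at 5 to 6 hours could be read at anywhere from 0.30 to 0.94 of its height. At an illustrative 0.80, a true ratio of 2 would read 2 × 0.80^0.25 = 1.89 with a quarter of fed subjects affected, 2 × 0.80^0.5 = 1.79 with half, and 1.60 with all. The documents do not exclude this, and the ECG rationale does not separate fed from fasted.

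These points are correct as far as they go, and so is the observation that no tablet tmax is printed. What is missing is any ground for the premise. No statement, figure or prior result in the documents puts a tablet peak after 4 hours, and the one relevant statement points to 4 hours or earlier. A protocol need not reproduce every earlier tmax, and the sponsor, which took the Cmax variability from Study TAK-831-1001, had those data available. The fed T1 data come from another formulation, a 100 mg dose and a high-fat meal; Regimen B uses a 237 mL, 355-calorie drink. They would inform the question without settling it.

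Nor is the extra draw free. It adds 2 × 4 = 8 mL per subject (412 to 420 mL) and 16 × 2 = 32 assays. No scheduled PD draw, ECG or vital-sign measurement falls at 6 hours to share it with. It would also need an amendment, IRB notification and possibly renewed consent.

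**Conclusion.** The concern does not hold. The 4-to-8-hour gap exists and is the same in both documents, but the grid is dense over the span in which the documents suggest the tablet peaks. If fed tmax has a median of about 2 to 3 hours, a 6-hour sample would recover under 1 percentage point of fed Cmax. If profiles are smooth, the loss stays within about 4.3% even for a subject who peaks inside the gap. A material bias needs fed peaks that are both late and sharp in a sizeable share of subjects.

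The study estimates the food effect with a 90% CI and sets no equivalence margin, so a shift of this order changes no decision. Whether to add a draw is a sampling preference on which reasonable designers could differ.

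This rests on reading the ECG rationale as placing the expected tablet peak within about 1 to 4 hours, and on assumed tmax distributions and profile shapes, since the documents give no tablet tmax. Evidence of frequent sharp fed peaks beyond 4 hours would change the conclusion; the documents contain none.

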9.1.13.2 Bioanalytical Methods

Plasma concentrations of TAK-831 will be measured by high-performance liquid chromatography with tandem mass spectrometry.

